7.6.5.2 Exploratory Efficacy Variables and Analysis

Duration of response (DOR) is defined as the time from the first tumor assessment that supports the subject's objective disease response to the time of disease progression or death due to any cause. Subjects who do not experience disease progression or death at the time of analysis will be censored using the same rules as described for PFS. DOR will be summarized using Kaplan-

Meier estimates, including the number of events, number of censored subjects, median and 95% confidence intervals.

Disease control rate (DCR) is defined as the percentage of subjects with sCR, CR, VGPR, PR, or stable disease (SD) per IMWG criteria; or MR per EBMT criteria ([Appendix B](#)). The analysis of DCR will be conducted in the same manner as ORR.

7.6.6 Safety Analyses

AEs will be coded according to the current Medical Dictionary for Regulatory Activities (MedDRA) and assessed for severity by the Investigator using the National Cancer Institute Common Terminology Criteria for Adverse Events (NCI-CTCAE) v. 4.03. TEAEs will be summarized by system organ class and preferred term and presented in decreasing order of frequency. Incidences of TEAEs and SAEs will be summarized overall and with respect to CTCAE grade and relationship to study drug. TEAEs leading to study drug discontinuation, dose reduction/interruption, and with an outcome of death will also be summarized. Incidence SAEs will be summarized overall and with respect to study drug.

Shifts from baseline in ECOG and changes in vital signs, ECG parameters, hematology and serum chemistry parameters from baseline to the EOT will be examined. Treatment-emergent changes from normal to abnormal values in key laboratory parameters will be identified. Changes in NCI toxicity grading will be presented using shift tables and listings of clinically significant values.

7.6.7 Pharmacokinetic/Pharmacodynamic Analyses

PK parameters will be assessed by non-compartmental analysis, including maximum concentration observed (C_{max}), area under the concentration time curve (AUC) to the end of the dosing interval ($AUC_{0-\tau}$), to infinite time ($AUC_{0-\infty}$), clearance, elimination half-life ($t_{1/2}$) and volume of distribution will be calculated, if data allow.

PK-PD modeling and simulation will be performed and may be used in support of dose escalation decisions and determination of the RP2D and dosing schedule; it will however be reported separately.

An explorative analysis of the relationship between exposure and body weight, if data allow, will be conducted, either graphically or as part of the PK-PD modeling activities.

Further exploratory analysis of PK data may be performed, such as the potential relationship with other covariates. These analyses will be described in a separate document outside of the SAP.

Exploratory biomarker analyses will be performed using descriptive biostatistics.

7.6.8 Research Laboratory Analyses

Analyses of research laboratory samples, tumor biopsies, and immune response data will be described separately outside the context of this protocol and the SAP.

7.6.9 Timing of Analysis

In Phase 1, all available data will be reviewed to enable dose-escalation and dose selection decisions.

In Phase 2, the primary analysis will be conducted after all subjects have completed at least 6 cycles of treatment and completed the EOT Visit, or discontinued study treatment. A supplemental analysis may be completed at the end of study that includes the cumulative data collected after the final analysis (i.e. through the Follow-up Period).

7.6.10 Data Monitoring Committee

There will be no formal Data Monitoring Committee for this study. Safety data and all unacceptable toxicities will be reviewed by the SRT comprised of participating Investigators in the study, the Medical Monitor, and representatives of the Sponsor.

8 ADVERSE EVENT REPORTING

AEs, SAEs, events of special interest, and pregnancy occurring during the protocol-specified timeframes defined in [Section 7.5.3.5](#) will be assessed and reported following guidelines provided in the following sections.

8.1 Adverse Events

An AE is defined as any untoward medical occurrence associated with the use of a drug in humans, whether or not considered drug related. An AE can therefore be any unfavorable and/or unintended sign (including an abnormal laboratory finding), symptom, or disease temporally associated with the use of an investigational medicinal product, whether or not related to the investigational medicinal product. All AEs, including observed or volunteered problems, complaints, or symptoms, are to be recorded on the appropriate eCRF.

Subjects should be instructed to report any AE that they experience to the Investigator. At each indicated visit, Investigators should make an assessment for AEs and record the event on the appropriate AE eCRF.

Wherever possible, a specific disease or syndrome rather than individual associated signs and symptoms should be identified by the Investigator and recorded on the eCRF. However, if an observed or reported sign or symptom is not considered a component of a specific disease or syndrome by the Investigator, it should be recorded as a separate AE on the eCRF. Additionally, the condition that led to a medical or surgical procedure (e.g. surgery, endoscopy, tooth extraction, or transfusion) should be recorded as an AE, not the procedure.

Any medical condition already present prior to the first dose of study drug should be reported in medical history unless the medical condition or signs or symptoms present at baseline change in severity or seriousness at any time during the study. In this case, it should be reported as an AE.

Clinically significant abnormal laboratory or other examination (e.g. ECG) findings that are detected during the study or are present at Screening and significantly worsen during the study should be reported as AEs. The Investigator will exercise his or her medical and scientific judgment in deciding whether an abnormal laboratory finding or other abnormal assessment is clinically significant. Clinically significant abnormal laboratory values occurring during the clinical study will be followed until repeat tests return to normal, stabilize, or are no longer clinically significant. Any abnormal test that is determined to be an error does not require reporting as an AE.

Examples of AEs include the following:

- Exacerbation of a chronic or intermittent preexisting condition, including an increase in frequency or intensity of the condition
- Signs, symptoms, or the clinical sequelae of a suspected interaction with another medical product

- Signs, symptoms, or the clinical sequelae of a suspected overdose of either investigational agent or a concurrent medication.

An overdose should not be reported as an AE or SAE; instead, the symptoms resulting from the overdose should be reported as the AE or SAE.

Examples of AEs do not include the following:

- Medical or surgical procedures (e.g. endoscopy, appendectomy); instead, the medical condition that led to the procedure is an AE
- Situations that are unwanted but in which an untoward medical occurrence did not occur (e.g. admissions for respite care)
- Anticipated day-to-day fluctuations of a pre-existing disease or condition (present or detected before enrollment) that does not worsen overall

A follow-up is required for all subjects with AEs until the event has been resolved or the condition has stabilized. In case of unresolved AEs, including significant abnormal laboratory values at the EOT visit assessment, these events will be followed up until resolution or until they become clinically not relevant.

8.1.1 Assessment of Adverse Events by the Investigator

The Investigator will assess the severity (intensity) of each AE and the potential relationship between the AE and the study drug.

8.1.1.1 Assessment of Severity

The severity of all AEs should be graded according to the NCI-CTCAE v. 4.03 (<http://ctep.cancer.gov/reporting/ctc.html>). For AEs not listed in the CTCAE, the following grading system should be used:

- Mild (CTCAE Grade 1): Transient symptoms, awareness of sign/symptom, but easily tolerated and no interference with subject's daily activities
- Moderate (CTCAE Grade 2): Marked signs/symptoms that interfere with subject's usual activities, but still acceptable
- Severe (CTCAE Grade 3): Incapacitating signs/symptoms which cause considerable interference with the subject's daily activities, unacceptable
- Life-threatening (CTCAE Grade 4): Life-threatening consequences; urgent intervention indicated
- Death (CTCAE Grade 5): Death-related AE

8.1.1.2 Attribution of Causality

The Investigator is obligated to estimate the relationship between the study drug(s) and the occurrence of each AE or SAE. The relationship (synonym: causality) is based on the Investigator’s clinical judgment regarding the likelihood that study treatment caused the AE and may include consideration of some or all of the following factors:

- Alternative possible causes of the AE, including the subject’s underlying disease or co-morbid conditions, other drugs, or other host and environmental factors
- The temporal sequence between the exposure to study treatment and the AE
- Whether the clinical or laboratory manifestations of the AE are consistent with known actions or toxicity of the study treatment
- Whether the AE resolved or improved with decreasing the dose or stopping the study treatment (i.e. dechallenge); or recurred or worsened with re-exposure to the drug (i.e. rechallenge).

The Investigator should consult the IB in the determination of the assessment. The Investigator should consider all possible etiologies for the AE and render a causality assessment based on the most likely contributing factor to the AE.

There may be situations when an SAE has occurred and the Investigator has minimal information to include in the initial report. However, the Investigator must assess causality for every event before the transmission of the SAE. The Investigator may change his or her opinion of the causality in light of follow-up information, amending the SAE report.

The assessment of the relationship between the AE and the study drug will be determined using one of the following attribution categories as outlined in the NCI Guidelines: Adverse Event Reporting Requirements (2013).

RELATIONSHIP	ATTRIBUTION	DESCRIPTION
Unrelated to investigational agent/intervention	Unrelated	The AE is clearly NOT related to the intervention
	Unlikely Related	The AE is doubtfully related to the intervention
Related to investigational agent/intervention	Possibly Related	The AE may be related to the intervention
	Probably Related	The AE is likely related to the intervention
	Definitely Related	The AE is clearly related to the intervention

AEs listed as possibly, probably, or definitely related are considered to have a suspected “reasonable causal relationship” to the investigational agent/intervention (ICH E2A). Per the ICH E2A and FDA guidelines, the expression "reasonable causal relationship" is meant to convey in general that there are facts (evidence) or arguments to suggest a causal relationship.

Additional guidelines in describing relationship:

- Related AEs follow a reasonable temporal sequence from the study drug administration and cannot be excluded as possibly or probably being caused by the study drug (e.g. existence of similar reports attributed to the suspected drug and/or its analogues; reactions attributable to the pharmacologic effect of the drug), and can be excluded as possibly being caused by other factors such as underlying disease, complications, concomitant drugs, or concurrent treatment. The AE can be fully explained by the administration of study treatment.
- Not Related: AE does not follow a reasonable temporal sequence from the study drug administration and can be reasonably explained by other factors, including underlying disease, complications, concomitant drugs, or concurrent treatment. Another factor is clearly the cause of the AE.
- For AEs occurring prior to initiation of study drug administration, the Investigator will assess relationship between the event and the protocol-required study procedures.

8.1.2 Disease-Related Events

Progression of the cancer under study is not considered an AE in this study unless it is considered treatment-related by the Investigator. The term "disease progression" should be recorded as an AE/SAE only if there are no other identifiable AEs/SAEs associated with the disease progression at the time of reporting. For events associated with disease progression, the relevant signs and symptoms should be reported using a diagnosis whenever possible rather than individual underlying signs and symptoms. When a clear diagnosis cannot be identified, each sign or symptom should be reported as a separate AE. If the events resulting from disease progression meet the criteria for an SAE (e.g. resulted in hospitalization, a life-threatening event, or death), the specific event(s) should be reported as an SAE(s)..

8.1.3 Events of Special Interest

Drug induced liver injury is considered an event of special interest in this study and is defined as serum chemistry laboratory values consistent with Hy's Law criteria (i.e. all 3 of the following must coexist):

- $ALT \text{ or } AST \geq 3 \times ULN$
- $Total \text{ bilirubin} \geq 2 \times ULN$
- $ALP < 2 \times ULN$

Laboratory values meeting all criteria for potential Hy's Law cases from the time of first study drug administration through the EOT visit should be reported following SAE reporting procedures [Section 8.3](#).

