7.1.1.1.1 Dose-limiting Toxicity Criteria

During Phase 1, the DLT evaluation period is defined as the first 28 days of treatment (Cycle 1). The occurrence of any of the toxicities presented in Table 7-2 will be considered a DLT unless clearly and incontrovertibly due to disease progression or extraneous causes. DLTs should be assessed and reported as directed in [Section 8](#).

Table 7-2. Criteria for Defining Dose-limiting Toxicities

Grade 5 event not clearly due to disease progression or extraneous causes
Hematologic toxicity defined as: 
 • Febrile neutropenia of any duration • Grade 4 neutropenia or thrombocytopenia that persists for >7 days, or Grade 3 thrombocytopenia associated with bleeding
Serum chemistry values consistent with Hy's Law criteria (all 3 of the following must co-exist): 
 • Alanine aminotransferase or aspartate aminotransferase $\geq 3\times$ institutional upper limit of normal (ULN) • Total bilirubin $\geq 2\times$ ULN • Alkaline phosphatase $< 2\times$ ULN
Grade 3 or higher infusion-related reaction per NCI CTCAE v 4.03
Any other Grade 3 or higher non-hematologic toxicity except: 
 • Grade 3 nausea, vomiting, or diarrhea that persists <72 hours with adequate antiemetic and other supportive care • Grade 3 fatigue <7 days

Emergent safety data will continue to be evaluated on an ongoing basis by the SRT.

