7.3.1 Inclusion Criteria

Individuals eligible to participate in this study must meet all of the following criteria:

1. Male or female, aged ≥ 18 years
2. Confirmed diagnosis of MM per IMWG criteria
3. Measurable disease as defined by one or more of the following:
 - Serum M-protein ≥ 0.5 g/dL
 - Urine M-protein ≥ 200 mg/24 hours
 - Serum Free Light Chain (FLC) assay: involved FLC level ≥ 10 mg/dL provided serum FLC ratio is abnormal
 - In cases where SPEP is unreliable, serum quantitative immunoglobulin (qIgA) ≥ 750 mg/dL (0.75 g/dL) is acceptable
4. Relapsed or refractory (Rajkumar et al. 2011) to 3 or more different prior lines of therapy for MM, including IMiDs, PIs, chemotherapies, or monoclonal antibodies, and not a candidate for, or intolerant to established therapy known to provide clinical benefit:
 - Relapse defined as progression of disease after an initial response (MR or better) to previous treatment, more than 60 days after cessation of treatment
 - Refractory disease defined as $< 25\%$ reduction in M-protein or progression of disease during treatment or within 60 days after cessation of treatment
5. Eastern Cooperative Oncology Group (ECOG) Performance Status of 0 – 1

6. Adequate organ and marrow function (i.e. without growth factors or transfusions) at Screening, as defined by the following laboratory parameters:

Hematologic	Renal	Hepatic
ANC \geq 1000/ μ L Platelets \geq 75,000/ μ L Hemoglobin \geq 7.5 g/dL Albumin \geq 3.0 g/dL	Creatinine clearance or eGFR >30 mL/min	AST/ALT \leq 3 \times ULN ALP \leq 2 \times ULN (ALP \leq 5 \times ULN for subjects with isozymes specific to bone) Bilirubin < 2 \times ULN; or Bilirubin \leq 3 \times ULN if due to Gilbert's disease ¹

¹ If diagnosis of Gilbert's disease has not been previously established, the following will be required: (a) evidence of prior isolated rises in bilirubin; (b) evidence that hyperbilirubinemia is due to rise in unconjugated bilirubin (indirect bilirubin); (c) normal CBC in previous 12 months; (d) blood smear and reticulocyte count; (e) evidence of normal transaminases and ALP in previous 12 months. ALP = alkaline phosphatase; ALT = alanine aminotransferase; ANC = absolute neutrophil count; AST = aspartate aminotransferase; eGFR = estimated glomerular filtration rate (Cockcroft-Gault); ULN = institutional upper limit of normal
		

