### 9.1. Adverse Events

After signing informed consent, and prior to the first study drug administration, any medical occurrence considered related to screening procedures (e.g. tumor biopsy, venipuncture) will be captured as an AE; all other medical events will be captured in the subject's medical history.

AEs will be assessed for severity using the NCI-CTCAE v. 4.03, relationship to BION-1301 (Definitely Related, Probably Related, Possibly Related, Unlikely Related, Unrelated), and seriousness (Yes, No). AEs will be considered treatment-emergent if the event occurs within the on-therapy period, the event was pre-existing and worsened in severity or became serious after the initiation of study drug.

An overview of treatment-emergent AEs (TEAEs) will be produced displaying counts and percentages of subjects with any incidences of: TEAEs, TEAEs with CTCAE Grade 3 or higher, TEAEs related to study treatment, TEAEs with CTCAE Grade 3 or higher related to study treatment, SAEs, TEAEs leading to study drug discontinuation, infusion-related reactions (IRRs), TEAEs leading to BION-1301 dose reduction/interruption; dose-limiting toxicities (DLTs), TEAEs of special interest (AESIs), and fatal TEAEs.

A separate overview of AEs identified as IRRs related to BION-1301 will be provided. This display will include the number of infusions received by subjects, the number of subjects having an IRR, total number of IRRs per subject, maximum IRR grade, and dose modifications resulting from IRRs.

Sponsor: Aduro Biotech, Inc.  
Protocol Number: ADU-CL-16  
Version and Date: Version 1.0, 18JUL2019

Adverse events will be coded based on the Medical Dictionary for Regulatory Affairs (MedDRA, Version 20.1) for reporting by system organ class (SOC) and preferred term (PT) in descending order of overall incidence. Events will be summarized. For these summaries, subjects with multiple AEs with the same SOC and/or PT will only be counted once at each level of summarization.

Summaries of adverse events by SOC and PT will include the following types:

- TEAEs;
- TEAEs related to study treatment (Definitely Related, Probably Related, or Possibly Related);
- TEAEs with CTCAE Grade 3 or higher;
- TEAEs with CTCAE Grade 3 or higher related to study treatment;
- BION-1301 IRR;
- TEAEs leading to dose reduction/interruption;
- SAEs;
- TEAEs leading to study drug discontinuation.

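### The bone-ALP and Gilbert's entry exceptions overlap a liver-injury definition that has no baseline provision, so the AESI count can miss some eligible subjects and be completed too easily in others

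*Protocol*

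**What the plan says.** **Event definition.** Protocol 8.1.3 names drug-induced liver injury as the event of special interest and requires that "all 3 of the following must coexist": ALT or AST ≥3×ULN, total bilirubin ≥2×ULN, ALP <2×ULN. The reporting trigger is "Laboratory values meeting all criteria for potential Hy's Law cases from the time of first study drug administration through the EOT visit", and such cases go through the SAE reporting procedure. Protocol 7.1.1.1.1, Table 7-2, uses the same three limits as a DLT criterion ("all 3 of the following must co-exist"). Neither place refers to the subject's baseline value.

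**Entry limits.** Inclusion criterion 6 (Protocol 7.3.1) asks for "Adequate organ and marrow function (i.e. without growth factors or transfusions) at Screening". Its hepatic limits are AST/ALT ≤3×ULN, ALP ≤2×ULN and bilirubin <2×ULN, with two exceptions:

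- ALP up to 5 × "ULN for subjects with isozymes specific to bone".
- Bilirubin up to 3 × "ULN if due to Gilbert's disease".

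**Analysis.** The adverse event overview in SAP 9.1 counts "TEAEs of special interest (AESIs), and fatal TEAEs". The SAP gives no definition of its own and no baseline rule for that row. SAP 9.2 plans summaries by visit, change from baseline, and shift tables to the worst CTCAE grade, each analyte separately.

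**The concern.** The definition is a conjunction of fixed limits, and the trial deliberately admits subjects who start on the wrong side of one of them.

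- **Missed cases.** A subject admitted with bone ALP of 2 to 5×ULN fails the ALP component for as long as ALP stays at that level. A marked combined rise in ALT and bilirubin would then not enter the AESI row, and would not trigger the SAE-procedure report that 8.1.3 otherwise makes automatic (24 hours under Protocol 8.3.1).
- **Cases completed too easily.** A Gilbert's subject admitted at 2 to 3×ULN has one of the three components in place before dosing. A transaminase change alone can complete the definition.

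Bone disease is central to this population: Protocol 7.5.5 says about 80% of myeloma patients have skeletal involvement on survey. That is not the proportion with raised ALP, but it shows why the bone exception was written.

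The incidence of DLTs and TEAEs is the primary endpoint in SAP section 2. With 21 subjects, an AESI count of zero is hard to read unless the reader knows whether every subject could have met the definition.

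**Working it through.** The documents state no figure to reproduce. The check sets the entry limits against the event limits (multiples of ULN).

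| Analyte | Entry limit (7.3.1, criterion 6) | Event component (8.1.3, Table 7-2) | Overlap |
|---|---|---|---|
| ALP, general | ≤2 | <2 | only at exactly 2.0, where the component fails |
| ALP, bone isozymes | ≤5 | <2 | 2.0 to 5.0, component fails |
| Bilirubin, general | <2 | ≥2 | none |
| Bilirubin, Gilbert's | ≤3 | ≥2 | 2.0 to 3.0, component already met |
| AST/ALT | ≤3 | ≥3 | only at exactly 3.0, component already met |

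Running ALT, ALP and bilirubin from 0.1 to 6.0×ULN in steps of 0.1 through both sets of limits gives the same result:

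- Neither exception: ALP blocks the definition only at 2.0. Bilirubin is never met at entry, and no eligible subject meets all three components.
- Bone exception: ALP blocks the definition from 2.0 to 5.0.
- Gilbert's exception: bilirubin is met at entry from 2.0 to 3.0. All three components are met at entry only if ALT or AST is exactly 3.0 and ALP is below 2.

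**Missed case, worked.** The rule is (ALT or AST ≥3) and (bilirubin ≥2) and (ALP <2).

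- ALT 10, bilirubin 4, ALP 3: true, true, false. Not an event.
- ALT 10, bilirubin 4, ALP 1.8: true, true, true. An event.

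Only ALP differs.

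**Easily completed case, worked.** A Gilbert's subject enters with bilirubin 2.5, ALP 1.0 and ALT below 3: false, true, true. If ALT reaches 3.0 with bilirubin still 2.5, the result is true, true, true.

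**What the SAP would show.** All the analytes are in the SAP 9.2 chemistry panel, but no planned table shows ALT/AST and bilirubin elevated together in the same subject. A reader would have to reconstruct this from the by-subject listings.

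**The case against.** The case on the other side is substantial, and much of it stands.

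- **Never.** A reader might infer that bone-ALP subjects can never be classified. The documents do not support that. The rule uses values from first dose to the EOT visit, so the block lasts only while ALP stays at or above 2×ULN.
- **Unchanged Gilbert's values.** A reader might infer that stable Gilbert's values would be reported as events. Raised bilirubin alone triggers nothing. Unchanged values qualify only if ALT or AST sits exactly at the entry maximum of 3.0×ULN with ALP below 2×ULN. Where Gilbert's was not previously established, criterion 6 also asks for evidence of normal transaminases and ALP in the previous 12 months. Protocol 8.1 sends conditions present before the first dose to medical history unless their severity or seriousness changes.
- **Detection.** Clinically significant laboratory abnormalities are still recorded as AEs (7.5.3.7, 8.1), and important medical events can be SAEs (8.2). SAP 9.1 tabulates Grade 3+ TEAEs. Causality must be assessed before an SAE report is sent (8.1.1.2).
- **DLTs.** Table 7-2 also makes other Grade 3+ non-hematologic toxicity a DLT, apart from listed exceptions, and 7.1.1.1.1 allows clearly extraneous causes to be discounted. What remains for DLTs is mainly combined elevations graded below 3.
- **Existing displays.** SAP 9.2 already summarizes direct and indirect bilirubin with change from baseline, so no further bilirubin table is needed.
- **Timing.** The study was terminated on 07 May 2019 and Phase 2 was not enrolled (SAP 3.1, 3.6). New protocol wording cannot change any dose decision already made.

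None of this puts a missed case into the AESI row or tells the reader which subjects could not meet the definition. The AE rules preserve the individual record; they do not repair the count.

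**Conclusion.** The overlap is real and follows directly from the stated limits. It arises almost entirely from the two exceptions. For all other subjects the limits only touch, at ALP 2.0 and AST/ALT 3.0×ULN.

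The consequence is confined mainly to the AESI count and the SAE-procedure reporting attached to it. The effect on DLTs is smaller because of the Grade 3+ catch-all and the extraneous-cause clause.

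The size in this trial cannot be computed, because the documents do not give the number of subjects who entered under either exception; it may be zero. One reclassified subject would move a rate by 1/3 = 33 percentage points in a cohort of three, 1/6 = 17 in a cohort of six, and 1/21 = 5 in the overall column. That is true of any single event at these sample sizes, so it does not measure this problem. Nor do the documents support an inference that any dose-escalation decision was wrong.

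The conclusion assumes that the SAP's AESI row follows the definition in Protocol 8.1.3, since the SAP offers no other. On that footing a modest reporting change is justified.

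**What to change.** **In SAP 9.1/9.2:**

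1. Keep the protocol-defined AESI row as it is.
2. Add a supplementary row counting subjects with concurrent on-therapy ALT or AST ≥3×ULN and total bilirubin ≥2×ULN, regardless of ALP. State what concurrent means; values from the same blood draw would be natural, as all three analytes are on one chemistry panel.
3. Flag subjects whose baseline ALP or total bilirubin (baseline as in SAP 5.5) is ≥2×ULN, and show the flag beside both rows.

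If the flag is empty, a footnote saying so largely closes the point.

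**In the protocol:** sections 7.1.1.1.1 (Table 7-2), 7.3.1 (criterion 6) and 8.1.3 must be reconciled by the sponsor. No threshold is proposed here for eligibility, the DLT rule or the event definition; the added row only reuses the protocol's existing ALT/AST and bilirubin limits for display.

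**Cost:** one table row and one baseline flag, from data already collected. The downside is that a row without the ALP condition may count some biliary or other non-drug cases. Those need narrative review, as do Gilbert's subjects whose bilirubin has not changed.
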